4.2. Exclusion Criteria

Patients with any of the following characteristics/conditions will not be included in the study:

1. Known active uncontrolled or symptomatic Central Nervous System (CNS) metastases, carcinomatous meningitis, or leptomeningeal disease as indicated by clinical symptoms, Cerebral edema, and/or progressive growth. Patients with a history of CNS metastases or cord compression are eligible if they have been definitively treated (eg, radiotherapy, stereotactic surgery) and are clinically stable off anticonvulsants and steroids for at least 4 weeks before randomization and have no evidence of progression at time of study enrollment.
2. Patients with advanced/metastatic, symptomatic, visceral spread, that are at risk of life-threatening complications in the short term (including patients with massive uncontrolled effusions [pleural, pericardial, peritoneal], pulmonary lymphangitis, and over 50% liver involvement).
3. Patients with an indwelling catheter that has an external component such as those used for drainage of effusion(s) or central venous catheter that is externally exposed (eg, peripherally inserted central catheter (PICC) line). Indwelling catheters that are fully internalized (eg, PORT-A-CATH®) are permitted.
4. Any other active malignancy within 3 years prior to randomization, except for adequately treated basal cell or squamous cell skin cancer, or carcinoma in situ.
5. Major surgery within 4 weeks prior to study entry.
6. Radiation therapy within 4 weeks prior to study entry.
7. Last anti-cancer treatment within 2 weeks (or 5 half-lives, whichever is shorter, unless the last immediate anti-cancer treatment contained an antibody based agent(s) (approved or investigational), then the interval of 4 weeks or 5 half-lives (whichever is shorter)) is required prior to receiving the investigational product.
8. Participation in other studies involving investigational drug(s) within 4 weeks (or 5 half-lives, whichever is shorter) prior to study entry.
9. Previous high-dose chemotherapy requiring stem cell rescue.
10. Active and clinically significant bacterial, fungal, or viral infection, including hepatitis B virus (HBV), hepatitis C virus (HCV), known human immunodeficiency virus (HIV) or acquired immunodeficiency syndrome (AIDS) - related illness. In equivocal cases, with positive serology, those patients with a negative viral load are potentially eligible provided the other entry criteria are met. This protocol excludes patients with active infections, as noted above. While SARS-CoV2 testing is not

mandated for entry into this protocol, testing should follow local clinical practice standards. If a patient has a positive test result for SARS-CoV2 infection, is known to have asymptomatic infection or is suspected of having SARS-CoV2, he/she is excluded. See [Appendix 6](#) for more information around SARS-CoV2.

11. Any of the following in the previous 6 months: myocardial infarction, congenital long QT syndrome, Torsades de pointes, arrhythmias (including sustained ventricular tachyarrhythmia and ventricular fibrillation), right bundle branch block and left anterior hemiblock (bifascicular block), unstable angina, coronary/peripheral artery bypass graft, symptomatic congestive heart failure (New York Heart Association class III or IV), cerebrovascular accident, transient ischemic attack, or symptomatic pulmonary embolism; deep venous thrombosis (DVT); arterial occlusive disease; ongoing cardiac dysrhythmias of National Cancer Institute (NCI) CTCAE Grade ≥ 2 , atrial fibrillation of any grade that is uncontrolled, or QTcF interval >470 msec at screening.
12. Hypertension that cannot be controlled by medications ($>150/100$ mmHg despite optimal medical therapy).
13. Known abnormalities in coagulation such as bleeding diathesis, or treatment with anticoagulants precluding intramuscular injections of fulvestrant or goserelin (if applicable).
14. Known or suspected hypersensitivity to active ingredient/excipients of PF-06873600, letrozole, fulvestrant and goserelin (or equivalent agent to induce chemical menopause).
15. Other acute or chronic medical or psychiatric condition, including recent (within the past year) or active suicidal ideation or behavior or laboratory abnormality that may increase the risk associated with study participation or investigational product administration or may interfere with the interpretation of study results and, in the judgment of the investigator, would make the patient inappropriate for entry into this study.
16. Investigator site staff members directly involved in the conduct of the study and their family members, site staff members otherwise supervised by the investigator, or patients who are Pfizer employees, including their family members, directly involved in the conduct of the study.
17. Pregnant female patients; breastfeeding female patients, female patients of childbearing potential and fertile male patients (Part 1A and Part 1C only) who are unwilling or unable to use 2 highly effective methods of contraception as outlined in this protocol for the duration of the study and for at least 28 days after the last dose of investigational product.
18. Active inflammatory gastrointestinal (GI) disease, known diverticular disease or previous gastric resection or lap-band surgery. Impairment of gastro-intestinal

function or GI disease that may significantly alter the absorption of PF-06873600, such as history of GI surgery with may result in intestinal blind loops and patients with clinically significant gastroparesis, short bowel syndrome, unresolved nausea, vomiting, active inflammatory bowel disease or diarrhea of CTCAE Grade >1. Gastroesophageal reflux disease under treatment with proton-pump inhibitors is allowed.

19. Current use of drugs as shown in [Appendix 5](#), which have a risk for QTc prolongation.
20. Current use or anticipated need for food or drugs that are known strong CYP3A4/5 inhibitors, including their administration within 5 half-lives of the CYP3A4/5 inhibitor, prior to first dose of investigational product. Current or anticipated use of moderate CYP3A4/5 inhibitors (including their administration within 5 half-lives of the CYP3A4/5 inhibitor, prior to first dose of investigational product) should be avoided if possible, and any use will need to be reviewed and approved by the Sponsor (See [Section 5.7](#)).
21. Current use or anticipated need for drugs that are known strong CYP3A4/5 inducers, including their administration within 5 half-lives of the CYP3A4/5 inducer, prior to the first dose of investigational product (See [Section 5.7](#)).

4.3. Lifestyle Requirements

In this study, female patients who are of childbearing potential, and fertile male patients as applicable to the study will receive PF-06873600 as a single agent or in combination with endocrine therapy, which currently has unknown teratogenicity/fetotoxicity so must be considered as suspected. Patients who are, in the opinion of the investigator, sexually active and at risk for pregnancy with their partner(s) must agree to use 2 methods of highly effective contraception throughout the study and for at least 28 days after the last dose of PF-06873600. The investigator or his or her designee, in consultation with the patient, will confirm that the patient has selected 2 appropriate methods of contraception for the individual patient (and her partner(s)) from the list of permitted contraception methods (see below) and will confirm that the patient has been instructed in their consistent and correct use. At time points indicated in the Schedule of Activities, the investigator or designee will inform the patient of the need to use 2 highly effective methods of contraception consistently and correctly and document the conversation, and the patient's affirmation, in the patient's chart. In addition, the investigator or designee will instruct the patient to call immediately if 1 or both of the selected contraception methods is discontinued or if pregnancy is known or suspected in the patient or partner.

Highly effective methods of contraception are those that, alone or in combination, result in a failure rate of less than 1% per year when used consistently and correctly (ie, perfect use) and include the following:

1. Established use of hormonal methods of contraception associated with inhibition of ovulation (eg, oral, inserted, injected, implanted, transdermal as approved by local

regulatory authority), provided the patient or male patient's female partner plans to remain on the same treatment throughout the entire study and has been using that hormonal contraceptive for an adequate period of time to ensure effectiveness.

2. Correctly placed copper-containing intrauterine device (IUD).
3. Male condom or female condom used WITH a separate spermicide product (ie, foam, gel, film, cream, or suppository). For countries where spermicide is not available or condom plus spermicide is not accepted as highly effective contraception, this option is not appropriate.
4. Male sterilization with absence of sperm in the post vasectomy ejaculate.
5. Bilateral tubal ligation/bilateral salpingectomy or bilateral tubal occlusive procedure (provided that occlusion has been confirmed in accordance with the device's label). All sexually active male patients must agree to prevent potential transfer to and exposure of partner(s) to drug through ejaculate by using a condom consistently and correctly, beginning with the first dose of investigational product and continuing for at least 28 days after the last dose of PF-06873600.

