Protocol Activity	Screening	Active Treatment Phase [†] - One Cycle = 28 days				End of Treatment/ Withdrawal [§]	Post-Treatment Follow-Up [*]
		Cycles 1 and 2		Cycles ≥3			
Study Day	Within 28 days prior to registration unless specified otherwise	Day 1 [‡]	Day 8	Day 15	Day 21	Day 1	
Visit Window			±3 days	±3 days	±3 days	±5 days	

7. **Contraception Check:** The investigator/designee, in consultation with the patient, will confirm that the patient has selected 2 appropriate methods of contraception for the individual patient (and her partner(s)) from the permitted list of contraception methods and will confirm the patient has been instructed in their consistent and correct use. Assessment should be performed within 7 days of C1D1, and Day 1 of every other cycle and at the EOT visit.

8. **Performance Status:** ECOG scale to be assessed within 14 days prior to the first dose of PF-06873600, and as indicated in the table above.

9. **Triplicate 12-lead Electrocardiography (ECG):**

Triplicate 12-lead ECG measurements will be performed at the following time points (single ECG is acceptable, as indicated below):

- Screening (single ECG);
- Cycle 1, Day 1: pre-dose (within 6 hours prior to the morning dose of PF-06873600), and 1 hour after the morning dose of PF-06873600;
- Cycle 1, Day 8: within 30 min prior to the morning dose of PF-06873600;
- Cycle 1, Day 15: pre-dose (within 30 min prior to the morning dose of PF-06873600), and 1 hour after the morning dose of PF-06873600;
- Cycle 2 and subsequent cycles, Day 1: within 30 min prior to the morning dose of PF-06873600;
- Cycle 2, Day 8: pre-dose (within 30 mins prior to the morning dose of PF-06873600);
- EOT (single ECG).

At each time point, (except those with single ECGs) 3 consecutive 12-lead ECGs will be performed approximately 2 minutes apart to determine mean QTcF interval. When coinciding with blood sample draws for PK, ECG assessment should be performed prior to blood sample collection, such that the blood sample is collected at the nominal time. If the mean QTcF is prolonged (≥ 501 msec), the ECGs should be re-evaluated by a qualified person at the institution for confirmation. Additional triplicate ECGs may be performed as clinically indicated.

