3.1.2. Part 1B PF-06873600 Dose Finding in Combination with Endocrine Therapy

After the single-agent PF-06873600 MTD/RDE has been determined for both the IR and MR formulations, enrollment will be initiated into Part 1B which will evaluate the PF-06873600 in combination with letrozole and in combination with fulvestrant in independent cohorts in women with HR-positive HER2-negative advanced or mBC. PF-06873600 will be administered orally on a continuous basis (unless the dose schedule has changed during Part 1A or Part 1C), while letrozole and fulvestrant will be administered per standard of care. Available safety and clinical data will be reviewed by the safety review team. The PF-06873600 dose in combination with letrozole may be decreased if determined to not be tolerable. The PF-06873600 dose de-escalation in combination with letrozole will follow the mTPI method. Similarly, the PF-06873600 dose in combination with fulvestrant may be decreased if determined to not be tolerable. The PF-06873600 dose de-escalated in combination with fulvestrant will follow the mTPI method. The MTD/RDE of each of the PF-06873600 formulations (IR and MR) in combination with the respective endocrine therapy (letrozole and fulvestrant) will be declared when at least 6 patients have been enrolled at a dose level that is predicted to be the MTD/RDE for each of the respective combination per the mTPI. Once the MTD/RDE of PF-06873600 in combination with letrozole and the MTD/RDE of PF-06873600 in combination with fulvestrant have been confirmed, a recommended dose for expansion for each combination will be declared and enrollment into Part 2 may be initiated. The decision to dose either the MR or IR or MR and IR formulation in Part 2 will be made following a careful review of all available clinical data and in alignment with C3661001 Safety Team.

Similar to Part 1A and/or Part 1C, dose escalation, all safety, PK and PD information from safety cohorts in Part 1B available will be used to determine the PF-06873600 MTD/RDE for the respective combination treatments.

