- Achieved postmenopausal status, defined as follows: cessation of regular menses for at least 12 consecutive months not due to prior chemotherapy, endocrine therapy or other pharmacologic cause and with no alternative pathological or physiological cause; postmenopausal status may be confirmed with a serum follicle-stimulating hormone (FSH) level. When there is a high FSH level, it should be confirmed that there is no other medical cause.
 - Have undergone a documented hysterectomy and/or bilateral oophorectomy.
 - Have medically confirmed ovarian failure.
 - Female patients who do not meet the above criteria (including female patients with tubal ligations) are considered to be of childbearing potential. Female patients with HR-positive HER2-negative advanced or mBC considered to be of child bearing potential must then undergo medically-induced menopause by treatment with luteinizing hormone-releasing hormone (LHRH) agonist goserelin, the gonadotropin releasing hormone (GnRH) agonist leuprolide (Lupron Depot[®]), or equivalent agents to induce chemical menopause (See [Section 4.3](#)).
12. Evidence of a personally signed and dated informed consent document indicating that the patient has been informed of all pertinent aspects of the study.

13. Willing and able to comply with scheduled visits, treatment plan, laboratory tests, and other procedures.

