5.8. Luteinizing Hormone Releasing Hormone (LHRH) Agonist

Pre/peri-menopausal women with HR-positive HER2-negative advanced or mBC can be enrolled if amenable to be treated with the LHRH agonist. Treatment with a LHRH agonist (eg, goserelin, leuprolide acetate or equivalent agents) should be used according to the prescribing information for all women who are pre- or peri-menopausal at study entry to induce chemical menopause throughout the study.

Patients not currently receiving an LHRH agonist prior to study entry must have commenced treatment with LHRH agonist at least 1 week prior to C1D1 for the monthly administration form and at least 3 weeks prior to C1D1 for patients receiving the LHRH on an every 3 month schedule.

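### The permitted contraception list lets HR-positive women stay on oestrogen-containing products while the protocol requires them to be in induced menopause

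*Protocol*

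**What the plan says.** **The contraception list.** Section 4.3 asks for two highly effective methods. Item 1 is "Established use of hormonal methods of contraception associated with inhibition of ovulation (eg, oral, inserted, injected, implanted, transdermal as approved by local" regulators, available to a patient (or a male patient's female partner) who "plans to remain on the same treatment throughout the entire study". It does not mention tumour type or HR status. Appendix 7.1 item 4(1) repeats the item for the J-LIC and splits it into combined (oestrogen plus progestogen) and progestogen-only products. The asterisks there mark only methods not approved in Japan.

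**The menopause rule.** Section 4.1 #11: "Female patients with HR-positive HER2-negative advanced or mBC considered to be of child bearing potential must then undergo medically-induced menopause". That sentence ends by referring the reader to 4.3. Section 5.8 calls for an LHRH agonist in "all women who are pre- or peri-menopausal at study entry to induce chemical menopause throughout the study".

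**The entry condition.** Exclusion #17 in 4.2 removes women of childbearing potential who are "unwilling or unable to use 2 highly effective methods of contraception as outlined in this protocol".

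**The check.** Under 4.3 the investigator confirms that the patient has "selected 2 appropriate methods of contraception for the individual patient (and her partner(s)) from the list of permitted contraception methods". Footnote 7 of the main Schedule of Activities sets the timing: "Assessment should be performed within 7 days of C1D1, and Day 1 of every other cycle and at the EOT visit".

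**Endocrine partner drugs.** Part 1B tests the letrozole and fulvestrant combinations "in independent cohorts in women with HR-positive HER2-negative advanced or mBC". All three Part 2 arms enrol HR-positive, HER2-negative disease and give one of the same two drugs.

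**The concern.** One section mandates ovarian suppression. The list it points to opens with a permission to continue ovulation-inhibiting hormones for the whole study. A site that reads the list literally could accept a combined pill in a woman whose oestrogen is being suppressed by the LHRH agonist or blocked by fulvestrant.

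The documents support the worry for oestrogen. Induced menopause is compulsory for these women, section 1.7 describes fulvestrant as an antagonist that blocks the growth-promoting action of oestrogens, and section 1.6 describes letrozole as an aromatase inhibitor approved for postmenopausal women. At stake is whether the affected patient receives the endocrine background the protocol intends. It is a matter of patient protection and internal consistency, and no analysis in the SAP depends on it.

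**Working it through.** No figure in the plan bears on this, so the check is textual.

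1. **Do the two rules cover the same women?** Section 4.1 #11 classes HR-positive women who are not postmenopausal, surgically sterile or in ovarian failure as of childbearing potential, and requires induced menopause. Exclusion #17 applies the two-method rule to women of childbearing potential. Section 4.3 narrows this to those whom the investigator judges sexually active and at risk of pregnancy. Neither section says that LHRH treatment lifts the contraception requirement. The overlap is therefore real: HR-positive, of childbearing potential, sexually active and at risk.

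2. **Does item 1 include oestrogen?** The main text names routes (oral, inserted, injected, implanted, transdermal) without limiting them to progestogen-only products. Appendix 7.1 item 4(1)a names the combined type outright.

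3. **Does another rule withdraw the permission?** Nothing in 4.2 addresses hormonal contraceptives. Section 5.7 restricts CYP3A4/5 inhibitors and inducers and advises caution with CYP3A4/5 and MATE substrates. Section 5.7.1 bars other anti-tumour treatment and certain herbal products. Sections 5.7.2 to 5.7.9 and 5.8 are silent. Item 1's reference to local approval concerns regulatory status. The product labels are not in the documents, so whether they add a bar cannot be judged here.

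4. **Does the investigator check close the gap?** It requires suitable methods but selects from the permitted list and does not mention HR status.

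5. **Who needs item 1?** TNBC and ovarian patients, and partners of male patients, are in Parts 1A and 1C, where the item is reasonable. Parts 1B and 2 enrol only HR-positive women, so any patient relying on item 1 there is HR-positive.

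6. **What is left in Japan?** Combined forms: oral, intravaginal*, transdermal*, injectable* = 4. Progestogen-only: oral*, injectable* = 2. Implanted*, from the parent line = 1. Total 4 + 2 + 1 = 7, of which 6 are marked as not approved, leaving 7 − 6 = 1: the combined oral pill. (Counting inserted* apart from intravaginal* gives 8 forms and 7 marked, with the same one left.) The J-LIC replaces inclusion criteria #1 and #2 but not #11, and encourages enrolment of metastatic breast cancer.

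7. **How many patients?** An affected woman must be HR-positive, of childbearing potential, judged sexually active and at risk of pregnancy, and already established on a hormonal method. The documents give no proportion for any of these conditions.

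**The case against.** The strongest defence is that a shared menu is not an instruction. The list serves every tumour type, nobody is told to use item 1, and a specific mandatory rule for HR-positive women should prevail over a general option. The investigators are treating HR-positive breast cancer with endocrine therapy, and they repeat the contraception check through the study. Several conditions must coincide before anyone is affected. Most of the endocrine-combination groups require prior endocrine therapy, which makes established hormonal contraception unlikely; Arm B is the exception. No document states that a combined pill impairs letrozole, fulvestrant or LHRH suppression. The sponsor terminated the study on 07 September 2022, and the Amendment 9 schedule has no contraception row and lists only PF-06873600 and fulvestrant.

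Much of this stands. The reach is small, the harm is inferred from the required menopause and fulvestrant's mechanism, and the remaining practical effect is slight. It does not remove the contradiction. Item 3 of the same list says when that option is not appropriate, so the protocol does state such limits; item 1 has none for HR-positive women. Relying on the investigator to overrule a listed permission is weaker than withdrawing it.

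**Conclusion.** The point holds as an inconsistency worth correcting, of low practical weight. A permission written for all tumour types contradicts treatment that the protocol makes compulsory for HR-positive women, and no other rule resolves it. Confidence in the textual finding is high. The number affected is undocumented and may be zero. The conclusion assumes that the list is read as applying to all patients, as written, and that no label outside these documents already bars the product.

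Three stronger readings are tempting but unsupported:

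- **A numerical ceiling.** A reader might add Part 1B (about 12 × 2 = 24) to Part 2 (about 40 + 30 + 30 = 100) and call 124 the maximum affected. That sum counts postmenopausal women, to whom the list does not apply. It omits HR-positive patients in Parts 1A and 1C, the biomarker cohorts and the J-LIC. It bounds nothing.
- **All hormonal methods are at fault.** The documents support the concern for oestrogen only. Tumours positive for progesterone receptor alone count as HR-positive under 4.1, which might prompt caution over progestogens, but that is inference.
- **Patients were exposed, or response results were distorted.** Nothing in the documents shows either.

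**What to change.** Add to 4.3 item 1 and to Appendix 7.1 item 4(1): *Oestrogen-containing contraceptives are not permitted in patients with HR-positive breast cancer (this does not apply to female partners of male patients).* Repeat the bar in 5.7, noting that LHRH/GnRH agonists are not affected. The sponsor should decide whether to extend it to progestogen-only products.

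The cost is wording in three places, with no new data, visits or analyses. Affected women lose one contraceptive option and may have to switch at screening. Where regular menses are absent, 7.1.1 asks for two methods for at least 1 month before the second pregnancy test, which may strain the 28-day screening window.

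In the J-LIC the loss is larger. Item 3 depends on a spermicide marked as not approved in Japan, so an HR-positive woman is left with items 2 (copper IUD), 4 (male sterilisation) and 5 (tubal procedure), and every pair (2+4, 2+5, 4+5) includes a surgical method. That cohort is only 3 to 6 patients with any solid tumour, on monotherapy, so the cost may fall on no one.
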